6.1.2 Treatment duration

All patients will be treated with HH2710 orally, beginning on Cycle 1 Day 1. Each cycle will have 21 days, until he/she meets the criteria for withdrawal ([Section 7.1.4.1](#) and [6.3](#))

6.2 Dose escalation guidelines

Phase I Dose escalation stage: the Bayesian optimal interval (BOIN) design incorporated with an accelerated titration will be used to assess the safety and tolerability, and furthermore, to help find the MTD, and/or to establish the RP2D combined with data from other sources.

6.2.1 Starting dose

The selection of the starting dose is based on the following consideration: 1) the PK-PD relationship established in human tumor xenograft mouse models, 2) the estimated human exposure of HH2710 obtained by allometric scaling modeling of dog and rat PK parameters, 3) and the toxicology studies data in rat and dog.

The starting dose for the Phase I study of HH2710 in patients with advanced tumors were calculated in accordance with the International Conference on Harmonization (ICH S9) guidance “Nonclinical Evaluation for Anticancer Pharmaceuticals”. The guidance recommends the starting dose should be based on either 1/10 of the severely toxic dose in 10% of animals (STD10) in rodent toxicity study or 1/6 of the HNSTD observed in non-rodent studies.

The starting dose for HH2710, for patients enrolled in this study, is set at 25 mg twice daily (BID), orally administered continuously. The selection of the starting dose follows the ICH S9 guidelines for choosing a starting dose for a first-in-human conducted in patients with cancer, and is shown in Table 6-1.

HH2710 safety profile was investigated in 4-week GLP toxicology studies in SD rats (15, 50 and 150/100 mg/kg/day) and Beagle dog (5, 15 and 60/30 mg/kg/day).

The rodent (SD rat) STD10 was considered to be between 50 and 100 mg/kg/day. Therefore 50 mg/kg/day has been used in this calculation. Converting this dose to a human equivalent dose (HED) and applying a 10-fold safety factor, translates to a safe starting dose of 48.6 mg/day.

The HNSTD in Beagle dog was 15 mg/kg/day. Converting this dose to a HED and applying the 6-fold safety margin, a safe starting dose of 81.15mg/day was calculated.

Consider the convenience of medication, the recommended safe starting daily dose has been adjusted to 50 mg/day in this protocol.

Table 6-3 Calculation of the MRSD for HH2710

Species	STD10 or HNSTD (mg/kg/day)	1/10 STD (rat) 1/6 HNSTD (dog)	Conversion Factor ^a	HED (mg/kg/day)	MRSD ^b (mg/day)
rat	50	5	0.162	0.81	48.6
dog	15	2.5	0.541	1.35	81.15

HED = (1/10 STD or 1/6 HNSTD) * Conversion Factor

^aConversion factor from 2005 FDA guidance [\[63\]](#)

^b Assumes a 60 kg human

6.2.2 Provisional dose levels

Table 6-4 describes the starting dose and the dose levels that may be evaluated during this study.

Table 6-4 Provisional dose levels

Dose level	Proposed daily dose* (BID/QD)	Increment from previous dose
-1**	25 mg QD	-50%
1	25 mg (BID)	(starting dose)
2	50 mg (BID)	100%
3	100 mg (BID)	100%
4	300 mg (QD)	50%
5	400 mg (BID/QD)	33%
7	600 mg (BID/QD)	50%
8	800 mg (BID/QD)	33%

Dose level	Proposed daily dose* (BID/QD)	Increment from previous dose
------------	----------------------------------	------------------------------

*It is possible for additional and/or intermediate dose levels to be added during the course of the study. Cohorts may be added at any dose level below the MTD in order to better understand safety, PK or PD. Proposed daily dose is the total dose each day with QD or BID dose frequency.

**Dose level -1 represent treatment doses for patients requiring a dose reduction from the starting dose level.

The starting dose level rationale see [Section 错误!未找到引用源。](#)

According to the non-clinical data and the modeling results, the preliminary plan of dose escalation including different doses (25mg, 50mg, and 100mg, BID;300mg QD, 400mg (BID/QD), 600mg (BID/QD), and 800mg (BID/QD)).

When 800mg QD escalation cohort and 600mg QD expansion cohort suspended due to safety concerns, 300mg QD dose level has been added to explore before or while proceeding with further dose escalation. In addition, an alternative BID dosing regimen starting from 200mg is also re-initiated to better understand the safety, tolerability and PK of HH2710 in dose escalation stage.

6.2.3 Guidelines for dose escalation and determination of (MTD/RP2D)

Phase I dose escalation stage:

[figure not shown]
The ATD + BOIN design is described as follows. Suppose the target toxicity rate for the MTD is $\phi = 0.3$ and the maximum sample size is 58 including up to 40 subjects for 25/50/100 mg BID + QD dose escalation cohorts (Part A) and up to 18 subjects for the additional BID dose escalation cohorts (Part B). Part B dose escalation will be conducted separately using BOIN design. We will enroll and treat patients in cohorts of size 3. To guide dose-escalation decisions, if the observed DLT rate at the current dose is ≤ 0.236 , the next cohort of patients will be treated at the next higher dose level; if it is ≥ 0.359 , the next cohort of patients will be treated at the next lower dose level. For the purpose of overdose control, doses j and higher levels will be eliminated from further examination if $\Pr(p_j > 0.3 | \text{data}) > 0.95$, where p_j is the true DLT rate of dose level j , $j = 1, \dots, 7$. When the lowest dose is eliminated, stop the trial for safety. The trial design is illustrated in Figure 6-1 and described through the following three steps:

1. Perform accelerated titration as follows: treat the first patient at dose level 1. If no \geq Grade 2 adverse event is observed, escalate the dose to the next higher level. Continue this one-patient-per-dose dose escalation process until any Grade ≥ 2 adverse event is observed or a dose level of 200 mg is reached, and then treat an additional 2 patients (at least 3 patients at that and all subsequent dose levels) at the first occurrence of a Grade 2 toxicity (i.e., the accelerated titration design should cease) or a dose level of 200 mg is reached. Hereafter, patients are treated in cohorts of size 3 as described in steps 2 and 3.
2. To assign a dose to the next cohort of patients, conduct dose escalation/de-escalation according to the rule displayed in Table 6-5. When using Table 6-5, please note the following:

- a. “Eliminate” means that we eliminate the current and higher doses from the trial to prevent treating any future patients at these doses because they are overly toxic.
- b. When we eliminate a dose, automatically de-escalate the dose to the next lower level. When the lowest dose is eliminated, stop the trial for safety. In this case, no dose should be selected as the MTD.
- c. If none of the actions (i.e., escalation, de-escalation or elimination) is triggered, we treat the new patients at the current dose.
- d. If the current dose is the lowest dose and the rule indicates dose de-escalation, treat the new patients at the lowest dose unless the number of DLTs reaches the elimination boundary, at which point terminate the trial for safety.
- e. If the current dose is the highest dose and the rule indicates dose escalation, treat the new patients at the highest dose.

3. Repeat step 2 until the maximum sample size (i.e., 40 for Part A or 18 for Part B) is reached or stop the trial if the maximum number of patients treated at the current dose reaches (i.e., 15 for Part A or 12 for Part B).

Figure 6-1 Flowchart for study conduct using the BOIN design

$$* \text{DLT rate} = \frac{\text{Total number of patients who experienced DLT at the current dose}}{\text{Total number of patients treated at the current dose}}$$

Table 6-5 Dose escalation/de-escalation rule for the BOIN Design

Number of patients treated at the current dose ^a	3 ^a	4 ^a	5 ^a	6 ^a	7 ^a	8 ^a	9 ^a	10 ^a	11 ^a	12 ^a	13 ^a	14 ^a	15 ^a
Escalate if # of DLT <=^a	0 ^a	0 ^a	1 ^a	1 ^a	1 ^a	1 ^a	2 ^a	2 ^a	2 ^a	2 ^a	3 ^a	3 ^a	3 ^a
Stay if # of DLT =^a	1 ^a	1 ^a	NA ^a	2 ^a	2 ^a	2 ^a	3 ^a	3 ^a	3 ^a	3/4 ^a	4 ^a	4/5 ^a	4/5 ^a
Deescalate if # of DLT >=^a	2 ^a	2 ^a	2 ^a	3 ^a	3 ^a	3 ^a	4 ^a	4 ^a	4 ^a	5 ^a	5 ^a	6 ^a	6 ^a
Eliminate if # of DLT >=^a	3 ^a	3 ^a	4 ^a	4 ^a	5 ^a	5 ^a	6 ^a	6 ^a	7 ^a	7 ^a	8 ^a	8 ^a	8 ^a

Dose expansion stage:

In order to further explore the safety, pharmacokinetics and efficacy during dose-escalation, dose expansion cohorts will be added in Phase I stage of the study. We plan to recruit up to 15 patients per cohort.

Patients with different cancer types enrolled in the dose expansion stage must have confirmation of specific MAPK pathway genetic alteration. During the study, the sponsor and investigators may request one or several dose levels and different dose regimens (QD, or BID) cohorts to further explore more PK and PD data. Such requests will be discussed with the investigator(s), sponsor and medical monitor(s), and should be based on all data available at that time, including safety and clinical activity, determinations of pharmacokinetics, pharmacodynamics, and cumulative toxicity. There are no specific stopping criteria for this part of the study, however, emerging data from the expansion phase will be monitored regularly by the data review committee.

MTD estimation:

After the escalation is completed, select the MTD based on the isotonic regression as specified in [64]. Specifically, select the MTD for which the isotonic estimate of the toxicity rate is closest to the target toxicity rate. If there are ties, select the higher dose level when the isotonic estimate is lower than the target toxicity rate and select the lower dose level when the isotonic estimate is greater than or equal to the target toxicity rate.

Biologically Effective Dose (BED)

The Biologically Effective Dose (BED) is the dose chosen by the sponsor and is based on all available preclinical data and clinical safety, efficacy, PK, and PD data.

Definition of RP2D

The RP2D is defined as the dose level chosen by the sponsor (in consultation with the investigators) for the dose extension in Phase II, based on safety, tolerability, efficacy, PK, and PD data collected during the dose escalation stage and/or phase I dose expansion of the study. RP2D maybe adjust if not suitable.

Determination of RP2D

Prior to beginning the phase II stage, there will be a comprehensive review of all safety, PK, and/or PD data from cycle 1 and subsequent cycles of phase I dose escalation and expansion to determine the risk/benefit profile of the MTD. Based on this review, the phase II stage will begin at the MTD/RP2D if the MTD is tolerated. The dose studied in phase II stage, MTD/RP2D, is defined as final recommended dose.

If the MTD is not found when the dose is increased to the maximum dose, or if the risk and benefit ratio of the MTD is not suitable for RP2D, then the Biologically Effective Dose (BED) is determined based on all available preclinical data and clinical safety, efficacy, PK and PD data. This BED was chosen as the recommended dose of Phase II recommended dose (RP2D).

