4.1 Description of study design

This is an open-label, multicenter, first-in-human Phase I/II study which is composed of a Phase I dose escalation stage, phase I dose expansion stage and a Phase II dose extension stage. HH2710 will be administered orally on a continuous twice daily (BID) schedule, 21 days as a “Cycle”

Phase I: Dose escalation

The accelerated titration (ATD) incorporated with Bayesian optimal interval (BOIN) design will be used to assess the safety and tolerability, and furthermore, to help find the maximum tolerated dose (MTD), and/or to establish the recommended phase 2 dose (RP2D) combined with data from other sources.

A maximum sample size is 58 patients for the dose escalation (ATD + BOIN). The total number of patients will depend upon the number of dose escalations actually needed.

Accelerated titration part:

One patient per cohort will be assigned to receive HH2710. The first three patients will take HH2710 once daily (QD) in cycle 1 day 1 for the single dose PK testing, from the second day, HH2710 will be administered orally on a continuous twice daily (BID).

The proposed dose level in accelerated titration stage is 25mg, 50mg and 100 mg twice daily (BID). It may be adjusted according to the available data. Because one subject at 25mg had adverse event grade ≥ 2 , the dose escalation process was shift to a BOIN design at 25mg dose level.

BOIN design part:

When there is an adverse event of grade ≥ 2 occurs, the dose escalation process will shift to a BOIN design, in which at least 3 patients per treatment cohort will be assigned (ATD + BOIN design details please see [Section 6.2.3](#))

Part A (25/50/100 mg BID + QD dose escalation cohorts):

To date 18 Jan 2022, 22 patients were enrolled in the dose escalation stage of 6 dose levels as 25mg BID (n=3), 50mg BID (n=3), 100mg BID (n=4), 400mg QD (n=4), 600mg QD(n=4), and 800mg QD (n=4), 4 patients were enrolled in the 600mg QD expansion cohort PK data from 22 enrolled patients showed HH2710 was slowly eliminated after oral administration, the accumulation of the systemic exposure of HH2710 at steady state was about 3-4 fold. The half-life ($t_{1/2}$) of HH2710 ranged from 8.42 to 10.9 hr, suitable for once daily dosing.

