Based on the safety data at 6 dose levels, HH2710 was well tolerated from 25 mg BID to 400 mg QD. However, 1 of 4 patients at 800 mg dose cohort experienced DLT (Grade 3 Acneiform rash). 3 of 26 patients developed Grade 1-2 eye toxicity, 2 patients were from the 600mg dose group,

and 1 from 800mg dose. Since the drug-related factor may have contributed, we have de-escalated to 300mg QD dose. And further dosing frequency and dose level may be adjusted based on available safety and PK data.

Part B (Additional BID dose escalation cohorts):

In order to determine the RP2D, additional BID dosing cohorts may also be evaluated based on available clinical data using BOPIN design starting from 200mg BID dose and the total sample size in Part B is up to approximately 18 subjects. After the escalation is completed, select the MTD based on the isotonic regression as specified in [64]. Specifically, select the MTD for which the isotonic estimate of the toxicity rate is closest to the target toxicity rate. If there are ties, select the higher dose level when the isotonic estimate is lower than the target toxicity rate and select the lower dose level when the isotonic estimate is greater than or equal to the target toxicity rate.

Dose expansion stage:

Additional up to 15 patients per cohort may be included in order to further explore the safety, PK and anti-tumor activities among biomarker-selected patients. The dose for provisional cohort of expansion phase will be based on available safety, PK/PD and preliminary efficacy data. Patients enrolled could have different cancer types but must be confirmed with specific MAPK pathway genetic alteration (the same requirement as in phase II). The total number of patients will depend upon the number of dose expansions necessary.

Phase II Dose extension:

This is an open-label, multicenter, dose extension stage at RP2D to explore the response of patients with particular tumor types harboring MAPK genetic alteration. A maximum of 108 patients will be enrolled.

Patients enrolled will be divided into four cohorts once RP2D is defined and each of them focuses on specific tumors with specific genetic alteration, which NGS (next generation sequencing) will be used to detect, described as follows:

- **Cohort 1:** Patients with *BRAF/NRAS* (mutation sites as follows: *NRAS* G13V, *NRAS* Q61, *BRAF* V600, *BRAF* G469A, L485W, L597Q, T599dup) mutated melanoma;

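### The elimination row of BOIN Table 6-5 does not follow from the stated overdose rule Pr(p_j > 0.3 | data) > 0.95 under any single Beta prior examined, and no DLT prior is stated

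*Protocol*

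**What the plan says.** Protocol 6.2.3 sets the target DLT rate at 0.3, with escalation at an observed rate of 0.236 or less and de-escalation at 0.359 or more. For overdose control, dose j and "higher levels will be eliminated from further examination if" Pr(p_j > 0.3 | data) exceeds 0.95. Neither document states a prior for p_j. The only Beta prior given, Beta(0.05,0.95), is for the Phase II response rate (Protocol 4.1 and 10.4).

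Step 2 of the same section has dosing follow Table 6-5. Its row "Eliminate if # of DLT >=" reads 3,3,4,4,5,5,6,6,7,7,8,8,8 for n = 3 to 15.

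Four other provisions decide how much the row matters:

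- Cohort size: "We will enroll and treat patients in cohorts of size 3".
- Note b, when the lowest dose is eliminated: the trial stops and "In this case, no dose should be selected as the MTD".
- Note d, when the table says de-escalate at the lowest dose: "treat the new patients at the lowest dose unless the number of DLTs reaches the elimination boundary".
- Cap per dose in step 3: "15 for Part A or 12 for Part B".

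**The concern.** The elimination boundary is the design's formal overdose control. The text defines it by a posterior probability and the table defines it by counts, and the two should agree. If they do not, the trial is run on a boundary that is not the one described to ethics committees and later reported.

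The direction of the mismatch also matters. Under the usual vague priors the table is laxer than the rule. Above the lowest dose, an affected cell still leads to de-escalation, but the dose stays open for re-entry. At the lowest dose, note d keeps patients there when the rule would have stopped the trial, and note b's bar on naming an MTD does not take effect.

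**Working it through.** **Inputs.** From Protocol 6.2.3: threshold 0.3, cut-off 0.95, cut-offs 0.236 and 0.359, cohorts of 3, caps of 15 (Part A) and 12 (Part B). The DLT prior is an assumption, so several were tried.

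**Step 1: the rows that reproduce.** Escalation, floor(0.236n), gives 0,0,1,1,1,1,2,2,2,2,3,3,3. De-escalation, ceil(0.359n), gives 2,2,2,3,3,3,4,4,4,5,5,6,6. Both match Table 6-5 for n = 3 to 15, which is 26 cells of 26.

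**Step 2: the elimination row.** With a Beta(a,b) prior and y DLTs in n patients, the posterior is Beta(a+y, b+n−y). The boundary is the smallest y with Pr(p > 0.3) > 0.95.

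| Prior | Row for n = 3 to 15 | Differs from table at n |
|---|---|---|
| Table 6-5 as printed | 3,3,4,4,5,5,6,6,7,7,8,8,8 | – |
| Beta(1,1) | 3,3,4,4,5,5,5,6,6,7,7,8,8 | 9, 11, 13 |
| Beta(0.5,0.5) | 3,3,4,4,5,5,6,6,6,7,7,8,8 | 11, 13 |
| Beta(0.3,0.7) | 3,3,4,4,5,5,6,6,7,7,7,8,8 | 13 |
| Beta(0.05,0.95) | 3,4,4,5,5,6,6,6,7,7,8,8,8 | 4, 6, 8 |

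Under the first three priors the table is one DLT higher than the rule in the cells listed. Under Beta(0.05,0.95) it is one DLT lower. The posterior probabilities in the critical cells are:

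| DLTs/n | Beta(1,1) | Beta(0.5,0.5) | Beta(0.3,0.7) | Beta(0.05,0.95) |
|---|---|---|---|---|
| 3/4 (table eliminates) | 0.9692 | 0.9699 | 0.9533 | 0.9236 |
| 5/9 (table does not) | 0.9527 | 0.9476 | 0.9317 | 0.9069 |
| 6/11 (table does not) | 0.9614 | 0.9572 | 0.9451 | 0.9261 |
| 7/13 (table does not) | 0.9685 | 0.9651 | 0.9557 | 0.9410 |

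**Step 3: could another prior reconcile them?** The row must eliminate at 3/4 but not at 7/13. Solving for b at fixed a:

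- a = 0.5 needs b < 0.978 and b ≥ 1.251.
- a = 1 needs b < 1.537 and b ≥ 1.999.
- a = 5 needs b < 6.999 and b ≥ 8.383.

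The two conditions conflict at all nine values of a tried, from 0.0001 to 5. A grid of 180,000 Beta priors (a up to 3, b up to 6) gave no full match; the best matched 12 of 13 cells. A contrived mixture, 75% Beta(1,1) plus 25% Beta(20,40), does match all 13 (3/4 = 0.9501, 7/13 = 0.9493). The mismatch is therefore shown for single Beta priors, not for every conceivable prior.

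**Step 4: settings that do fit.** With a uniform prior the printed row is reproduced by a cut-off of 0.9686–0.9692 at threshold 0.30, or by a threshold of 0.325–0.333 at cut-off 0.95. With Jeffreys the ranges are 0.9652–0.9698 and 0.320–0.329.

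**Step 5: consequence at the looks the design uses.** At multiples of 3, none of the uniform, Jeffreys and Beta(0.3,0.7) rows differs from the table except the uniform row, at n = 9. After 5/9 at the lowest Part B dose the cap allows one more cohort of 3. That cohort leaves the dose open, at 5 or 6 of 12 (42–50%), if it has 0 or 1 DLT. The probability is (1−p)³ + 3p(1−p)²:

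- p = 0.3: 0.343 + 0.441 = 78%
- p = 0.4: 0.216 + 0.432 = 65%
- p = 0.5: 0.125 + 0.375 = 50%

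The next table enumerates all cohort-of-3 paths exactly, assuming three doses with 200 mg BID lowest, N = 18 and a cap of 12. The first two columns after the rates give the probability of stopping for toxicity; the last gives how often 5/9 occurs at the lowest dose.

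| True DLT rates | Printed row | Rule, uniform prior | 5/9 at lowest dose |
|---|---|---|---|
| .1/.25/.4 | 0.20% | 0.25% | 0.04% |
| .2/.35/.5 | 2.3% | 3.1% | 0.9% |
| .3/.45/.6 | 9.7% | 12.9% | 4.1% |
| .4/.55/.65 | 25.6% | 31.7% | 9.4% |
| .5/.6/.7 | 49.1% | 56.1% | 13.9% |

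Under Jeffreys or Beta(0.3,0.7) the difference is zero in every row.

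**The case against.** The arithmetic is not in dispute; the consequences are.

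- **A high count at the lowest dose is not peculiar to this defect.** Every corrected row proposed here still has 7 at n = 12, so 5/12 or 6/12 reached through 4/9 stays eligible as MTD after correction. At .4/.55/.65 the lowest dose ends there without elimination in 29.3% of trials under the printed row and 23.3% under the uniform-prior row. This stands: the defect adds to that risk and does not create it. The 78/65/50% figures are also conditional on 5/9, which is uncommon.
- **The operational effect needs a uniform prior, and 200 mg BID treated as the lowest dose.** Lower BID doses had already been tested, and Protocol 6.2.3.2 allows intermediate or lower cohorts. This stands as a limit on size.
- **Table 6-5 is not the only safeguard.** Dose-decision meetings (6.2.3.1), the Safety Monitoring Committee (6.2.4) and the option of a biologically effective dose in place of the MTD (6.2.3) all intervene. True, but none of them makes the table agree with the rule.
- **The 0.969 and 0.33 explanations are back-fits.** Correct; they are inferences. Under Beta(0.3,0.7) a single wrong digit at n = 13 would account for the row equally well. A cited source might name a prior, but no single Beta prior examined closes the gap.
- **No effect on patients has been shown.** At the January 2022 cut-off the escalation levels held 3 or 4 patients each, for example "100mg BID (n=4), 400mg QD (n=4), 600mg QD(n=4), and 800mg QD (n=4"), and 600 mg QD had 4 more in expansion, 8 in all. Part B starts at the same daily dose as 400 mg QD, and "HH2710 was well tolerated from 25 mg BID to 400 mg QD". SAP section 7 records that the programme is stopped. All of this stands.

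**Conclusion.** The concern holds. Table 6-5's elimination row contradicts the rule it is meant to implement, and naming an ordinary prior would not repair it. Because the two companion rows match in all 26 cells, settings other than those stated for this row are the likelier explanation than a damaged table, though the documents do not show how it was produced.

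The practical effect is probably small. At cohort-of-3 looks it is confined to 5/9 under a uniform prior. On the three-dose Part B assumption, it lowers the chance of stopping for toxicity by about 3 percentage points at .3/.45/.6 (12.9 − 9.7 = 3.2) and 7 points at .5/.6/.7 (56.1 − 49.1 = 7.0). Cells n = 11 and 13 come into play only if cohort sizes depart from 3, as the levels with 4 patients show can happen. It should be corrected because it is a safety threshold and the correction is almost free.

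**What to change.** Do one of the following:

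1. State the DLT prior and regenerate the row at 0.30/0.95, using the matching row from the first table above (for example 3,3,4,4,5,5,5,6,6,7,7,8,8 for a uniform prior).
2. Keep the printed row and correct the text to the prior, threshold and cut-off actually used. If the prior was uniform, that means a cut-off of about 0.969 at 0.30, or a threshold of about 0.33 at 0.95.

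Then check any dose that reached 9 or more patients after January 2022 against the corrected row and report whether any decision would have changed. The cost is one table row or one sentence, with no extra patients. With the programme stopped, a note in the study report is sufficient.

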According to the non-clinical data and the modeling results, the preliminary plan of dose escalation including different doses to determine the safety, tolerability, PK/PD of HH2710. Dosing frequency and dose level may be adjusted after Safety Monitoring Committee (SMC) discussion during the study base on available safety, PK/PD and preliminary efficacy data. To date 18-Jan, 2022, 22 patients were enrolled in the dose escalation stage of 6 dose levels as 25mg BID (n=3), 50mg BID (n=3), 100mg BID (n=4), 400mg QD (n=4), 600mg QD (n=4), and 800mg QD (n=4), 4 patients were enrolled in the 600mg QD expansion cohort. PK data from 22 enrolled patients showed HH2710 was slowly eliminated after oral administration, the accumulation of the systemic exposure of HH2710 at steady state was about 3-4 folds. The half-life ($t_{1/2}$) of HH2710 ranged from 8.42 to 10.9 hrs, suitable for once daily dosing. The HH2710 systemic exposure showed a

dose-related increase from 25mg BID to 800mg QD. No apparent dose- or time-dependence of PK was observed upon single and multiple dose administration. Based on the available PK and safety data, the sponsor decided to suspend 800mg QD escalation cohort and 600mg QD expansion cohort.

To determine the recommended phase II dose (RP2D), the sponsor plans to further evaluate the tolerability, biological activity, PK/PD, and preliminary efficacy of HH2710 at more dose levels with different dosing frequencies (QD or BID). In addition to the current QD dosing cohorts (designated as Part A), sponsor may add BID dosing cohorts in Part B based on available evidence. Part B will start from 200mg BID dose level. During the study, the Sponsor and Investigators may request that one or several dose level cohorts to be expanded to get more PK/PD and safety data, or that insert an intermediate dose between 2 adjacent planned escalation doses to be explored. Such requests will be discussed with the Investigator(s), Sponsor and Medical Monitor, and should be based on all data available at that time, including safety and clinical activity, determinations of pharmacokinetics, pharmacodynamics, and cumulative toxicity.

3 Objectives and endpoints

Objectives and related endpoints are described in [Table 3-1](#) below.

Table 3-1 Objectives and related endpoints

Objective	Endpoint	Analysis
Primary		Refer to Section 10.5
Phase I :	Phase I:	

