4.2 Timing of interim analyses and design adaptations

There are three planned interim analyses during the study. One is performed for the determination of RP2D when Phase I completes. The other two are conducted for futility evaluation for the first 23 patients in each of cohort 1 and cohort 2 when these patients have completed the assessment. Any additional interim analyses can be conducted as requested by the sponsor for safety and/or efficacy monitoring while the study is ongoing.

A sponsor-led data review committee will be used during the study. In Phase I, safety data will be reviewed by the committee after a minimum of 3 patients have been enrolled into each dose level and received treatment. Once the dose escalation stage completes, the committee will review safety data as well as data from other sources (e.g. efficacy, PK/PD) to determine the RP2D for Phase II.

In Phase II, the efficacy review will be conducted for each cohort by the committee when cohort 1 and cohort 2 have recruited and completed the assessment for the first 23 patients. For safety, the committee will review data when every 6 or 12 patients who have recruited and received treatments in all cohorts. Following the data review, the committee will decide as to whether the cohort may continue, whether amendment(s) to the protocol should be implemented, or whether the study should be stopped. The proposed interim analysis sketch map for cohort 1 and 2 is shown below in [错误!未找到引用源。2](#).

Figure 4-2 the proposed interim analysis sketch map for cohort 1 and 2

Notes: SD \geq 6 months

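### The Phase I expansion stage has no monitoring interval or boundary, and the plan does not say whether expansion DLTs count toward the overdose rule or the isotonic MTD estimate

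*Protocol*

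**What the plan says.** **Escalation.** Protocol 6.2.3 sets a target DLT rate of 0.3 and, for overdose control, states that "doses j and higher levels will be eliminated from further examination if" the posterior probability of a DLT rate above 0.3 exceeds 0.95. Table 6-5 gives the elimination counts for 3 to 15 patients at a dose. Note (a) to step 2 removes an eliminated dose, and those above it, from the whole trial. The cap per dose is 15 in Part A and 12 in Part B.

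**Expansion.** The same section allows up to 15 patients per cohort, added while escalation is under way, and says: "There are no specific stopping criteria for this part of the study". The sentence goes on to promise regular monitoring by the data review committee, with no interval, count or threshold.

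**Use of DLTs.** Protocol 6.2.4 brings DLTs into the BOIN for escalation decisions. The DLT rate under Figure 6-1 divides by all patients treated at the current dose, without saying whether expansion patients are included. The MTD is selected by isotonic regression once escalation is complete; the input data are not specified further. The RP2D paragraphs do call for safety data from both escalation and expansion.

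**Review triggers elsewhere.** For Phase II, Protocol 4.2 states an interval: "For safety, the committee will review data when every 6 or 12 patients who have recruited and received treatments in all cohorts". For Phase I, Protocol 10.5.1 has a review after at least 3 patients per dose level, but the opening of Section 10 uses Phase I to mean the BOIN dose-finding phase. SAP 7.1 adds no expansion rule, and SAP 8.8.1.2 plans only a DLT listing.

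**History.** Protocol 2.3 reports that "the sponsor decided to suspend 800mg QD escalation cohort and 600mg QD expansion cohort".

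**The concern.** An expansion cohort can hold more patients at a candidate RP2D than escalation did: up to 15, against 4 in escalation at each of 400, 600 and 800 mg QD by the January 2022 cutoff. Escalation patients are covered by a tabulated rule. If DLTs accumulate during expansion, nothing binding follows, even when the pooled data at that dose meet the sponsor's own 0.95 criterion. Because elimination also closes higher doses, uncounted expansion DLTs at one dose could bear on whether a higher escalation dose stays open.

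There is also an analysis issue. If expansion DLTs stay out of the isotonic fit, the MTD estimate at an expanded dose rests on a handful of patients although more data exist. If they are meant to go in, the plan should say so, because DLT evaluability in Protocol 6.2.4 (80% compliance in Cycle 1) is not stated to apply to expansion patients.

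**Working it through.** **Inputs.** Target φ = 0.3, thresholds 0.236 and 0.359, the 0.95 rule and the Table 6-5 elimination row 3, 3, 4, 4, 5, 5, 6, 6, 7, 7, 8, 8, 8 for n = 3 to 15 (all Protocol 6.2.3); expansion size up to 15. Assumed, because the documents do not give them: the Beta(1,1) prior, the true DLT rates, the escalation counts at the expanded dose, and looks every 3 expansion patients.

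**1. Reproduce the plan's figures.** With the usual BOIN alternatives φ1 = 0.6φ = 0.18 and φ2 = 1.4φ = 0.42:
- λe = ln(0.82/0.70) / ln[(0.3 × 0.82)/(0.18 × 0.70)] = 0.1582/0.6690 = 0.2365
- λd = ln(0.70/0.58) / ln[(0.42 × 0.70)/(0.3 × 0.58)] = 0.1881/0.5245 = 0.3585

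These match the protocol. The escalate and de-escalate rows reproduce in all 13 columns.

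The elimination boundary is the smallest x with Pr(p > 0.3) > 0.95 when p ~ Beta(1 + x, 1 + n − x). At n = 15, 8 DLTs give 0.974 and 7 give 0.926, so 8 is confirmed. Ten of 13 columns reproduce. At n = 9, 11 and 13 the rule gives 5, 6 and 7 (posteriors 0.953, 0.961, 0.969), where the table prints 6, 7 and 8. Beta(0.5,0.5), Beta(0.3,0.7) and Beta(0.6,1.4) do not reproduce the whole row either.

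**2. Pooled rule.** With 4 escalation patients, looks after 3, 6, 9 and 12 expansion patients fall at pooled n = 7, 10, 13 and 16. Table 6-5 gives 5, 6 and 8 for the first three. It ends at 15, so the 0.95 rule supplies n = 16: 8 DLTs (posterior 0.960). A look after the 15th patient (n = 19, boundary 9, posterior 0.952) comes too late to reduce enrolment in that cohort.

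**3. One case by hand: 0/4 in escalation, true rate 50%.**
- n = 7: 5 DLTs needed from 3 patients; impossible.
- n = 10: all 6 must have a DLT: 0.5⁶ = 0.0156.
- n = 13: 5 of the first 6, then 3 of 3: (6/64) × (1/8) = 0.0117.
- n = 16: at least 8 of 12 without an earlier crossing: 0.1682.
- Sum: 0.1956, or 20%. With Table 6-5 alone, which has no n = 16 column, the sum stops at 0.0273, or 2.7%.

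**4. Probability of a pause before the 15th expansion patient** (exact binomial recursion):

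| True DLT rate | Pooled, 0/4 | Pooled, 1/4 | Expansion cohort alone |
|---|---|---|---|
| 20% | 0.1% | 0.5% | 2.3% |
| 30% | 1.0% | 4.3% | 9.8% |
| 40% | 5.8% | 17% | 26% |
| 50% | 20% | 40% | 49% |
| 60% | 44% | 67% | 74% |

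At a 50% rate, expected expansion enrolment is 14.3 (0/4) or 13.1 (1/4), against 15 if the cohort is simply filled.

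**5. Precision.** With no events, the exact 95% upper limit is 1 − 0.025^(1/n). For 0/4 it is 1 − 0.025^0.25 = 60%; for 0/8 it is 1 − 0.025^0.125 = 37%. This is the gain from adding the 4 expansion patients to the 4 escalation patients at 600 mg QD, if none of the 8 had a DLT (assumed).

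**The case against.** The strongest reply is that discretion is in place and has worked. Protocol 6.2.3 has the committee monitor expansion data, Protocol 6.2.4 sets up a safety monitoring committee and requires immediate notice of unexpected Grade 3 or higher events, and the 600 mg QD expansion was suspended with 4 patients in it. The toxicity singled out for that dose group is two Grade 1-2 eye events, which would not have crossed Table 6-5. Committee judgement acted sooner than a numeric rule would have. This stands: a boundary is a floor under that judgement and cannot replace it. It does not answer what must happen when the sponsor's own criterion is met, or which patients are counted.

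A reader might also infer four stronger points that the documents do not support.
- That a dose eliminated in escalation could still be filled to 15. Note (a) in Protocol 6.2.3 takes it out of the trial.
- That the RP2D ignores expansion data. Protocol 6.2.3 requires review of both stages; only the isotonic MTD input is unclear.
- That a rule would halt 49% or 74% of overly toxic cohorts. Those figures hold only for an expansion cohort monitored alone; pooling with clean escalation data makes the rule much milder.
- That the review every 6 or 12 patients covers expansion. In Protocol 4.2 it belongs to Phase II.

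A fair point on cost: evaluability needs 80% Cycle 1 compliance, expansion patients are not replaced (Protocol 7.1.4.3), and looks every 3 patients over a 21-day window mean waiting or deciding on immature data.

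**Conclusion.** The concern holds in a limited form. Expansion monitoring has no stated interval or boundary, and the documents leave open whether expansion DLTs enter the overdose rule and the isotonic fit. The gap is confined to toxicity that emerges during expansion.

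The protective gain from the pooled rule is moderate: a pause probability of 20% to 40% at a 50% true DLT rate and 44% to 67% at 60%, with false pauses of about 1% to 4% at the 30% target. These figures rest on assumed true rates, an assumed 0/4 or 1/4 in escalation, a Beta(1,1) prior and looks every 3 patients. The comparison with 15 also supposes that the committee would not act on its own, so it is an upper bound on the benefit.

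SAP Section 7 reports that the programme has stopped and the study ended early. The enrolment rule now matters mainly for the record and for any reuse of the design; the pooling and isotonic-fit question still bears on this study's analysis.

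**What to change.** Reconcile Protocol 6.2.3 and 6.2.4, and carry the result into the SAP:
1. State that expansion patients are DLT-evaluable in Cycle 1 under the Protocol 6.2.4 definition.
2. Pool their DLTs with escalation data at the same dose and regimen, and enter the pooled counts in the isotonic fit.
3. Check the existing 0.95 posterior rule at stated intervals, for example every 3 expansion patients. State its prior and extend it beyond n = 15, since pooled counts outrun Table 6-5. A crossing pauses enrolment to that cohort for committee review; the committee keeps its discretion to act earlier.
4. Reconcile Table 6-5 with the 0.95 rule at n = 9, 11 and 13, or state the prior or adjustment that produces the printed row.

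For the analysis of the terminated study, items 1 and 2 suffice: one SAP sentence saying whether expansion DLTs are in the tally and the fit.

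**Cost.** Wording, plus DLT classification of Cycle 1 data from visits already in Table 7-1. In a running trial there would also be occasional false pauses (about 1% to 4% at a 30% rate) and some enrolment delay while Cycle 1 data mature.
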